### **3.2.3. DDI Sub-study with Anti-fungal Agents that are Strong CYP3A Inhibitors**

#### **3.2.3.1. Sub-Study Rationale**

Since AML subjects are at a high risk for fungal infections, to reduce the likelihood and severity of fungal infections, azole antifungal agents such as fluconazole, posaconazole and voriconazole are commonly administered. However, these azole compounds carry DDI risks because of their inhibitory effect on CYP3A enzymes. Based on nonclinical assessment, DS-1594b is a CYP3A substrate (see Section 2.4.2 ), thus DDI assessment for DS-1594b and antifungal agents is necessary to identify the DS-1594b dosing regimen that can be concomitantly given with antifungals and potentially extend to other strong CYP3A inhibitors. This DDI assessment is also aligned with the recommendation from the FDA Industry Guidance for developing drugs and

biological products for AML treatment (Aug 2020). The guidance recommends studying DDI with moderate and strong CYP3A inhibitors early in clinical development if the investigational AML drug is a CYP3A substrate, to determine dose modification, if needed, when concomitantly administered with moderate and/or strong CYP3A inhibitors.

### 3.2.3.2. Sub-study Design

Following dosing in Phase 1 Dose Escalation and MTD declaration, approximately 12 additional subjects will be enrolled into a drug-drug interaction (DDI) sub-study within the Phase 1 portion of the study at a predetermined dose level (at least 50% below the RP2D, as recommended by the SRC) to assess the effect of multiple doses of antifungal agents (i.e. posaconazole [N ~ 6], voriconazole [N ~ 6]) that are strong CYP3A inhibitors, on the steady-state PK of DS-1594b. Based on preliminary assessment using physiologic-based modeling, the magnitude of PK increase of DS-1594b ranges from 30% (with posaconazole) to 2-fold (with voriconazole).

This estimate will be further assessed based on emerging clinical and nonclinical data and the information will be provided to the SRC for consideration in dose selection. Nonetheless, the dose will be at least 50% below the declared RP2D. These subjects can be the same subjects included in the Phase 1 expansion for RP2D determination.

This DDI sub-study is a single sequence, crossover design. Enrollment will complete on the posaconazole sub-study before enrollment will begin on the voriconazole sub-study. Subjects will receive twice-daily or daily oral dosing of DS-1594b alone at the assigned dose from Cycle 1 Day 1 to Cycle 1 Day 8. On Cycle 1 Day 9 to Cycle 1 Day 18, subjects will receive the same assigned DS-1594b dose with either (a) 300 mg oral posaconazole twice on Cycle 1 Day 9 and once daily on Cycle 1 Day 10 to Cycle 1 Day 18 or (b) 400 mg oral voriconazole twice on Cycle 1 Day 9 and 200 mg twice daily from Cycle 1 Day 10 to Cycle 1 Day 18.

The anti-fungal agents are planned to be given for 10 consecutive days as stated above to ensure steady-state is reached in order to maximize inhibitory effect on CYP3A-mediated metabolism of DS-1594b. After completion of the sub-study (Cycle 1 Day 18 is the last day of the sub-study), subjects will continue with DS-1594b dosing alone starting on Cycle 1 Day 19. PK sampling timepoints of DS-1594b are outlined in [Table 17](#)[Table 17](#).

Formatted: C-Hyperlink

**Note:** If the use of posaconazole is essential for subject care during the dose escalation phase (i.e. prior to MTD/RP2D declaration), the subject can enter the DDI sub-study sooner, starting from the third dose escalation cohort. Voriconazole is not allowed as DDI perpetrator prior to MTD declaration given it is a more potent CYP3A inhibitor compared to posaconazole. To avoid interference with the DLT evaluation period (first 28-day cycle), subjects will receive oral twice daily or daily dosing of DS-1594b alone at the assigned dose for the entire Cycle 1. Starting on Cycle 2 Day 1 to Cycle 2 Day 10, subjects will receive either the same assigned DS-1594b dose provided that dose level has been declared safe from the DLT evaluation, or at one dose level lower with 300 mg oral posaconazole twice on Cycle 2 Day 1 and once daily on Cycle 2 Day 2 to Cycle 2 Day 10. After completion of the sub-study (Cycle 2 Day 10 is the last day of the sub-study), subjects will continue with DS-1594b dosing alone starting on Cycle 2 Day 11. PK sampling timepoints of DS-1594b for these subjects are outlined in [Table 18](#)[Table 18](#). These subjects will contribute to the overall sample size of ~ 12 for DDI sub-study.

Formatted: C-Hyperlink, Font: Italic

The entry criteria for subjects in DDI sub-study will be the same as all other subjects, except for additional concomitant medications restrictions for CYP3A modulators and gastric reducing agents (see Section 4.2 ).

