**Table 4: Dose escalation/de-escalation rule for the Boin design**

[figure not shown]
Number of subjects treated at current dose	3	4	5	6	7	8	9
Escalate if number of DLTs is less than or equal to	0	0	0	0	1	1	1
De-escalate if number of DLTs equal to or greater than	1*	1*	2	2	2	2	3
Eliminate if number of DLTs equal to or greater than	2	3	3	3	4	4	4

Note. # of DLT is the number of subjects with at least 1 DLT in the first 28 days of dosing. Observations from IPDE will not be considered (Section 6.9). When none of the actions (i.e., escalate, de-escalate or eliminate) is triggered, stay at the current dose for treating the next cohort of subjects. \*The SRC can decide to enroll an additional 3 subjects at this dose level. In case the multiple dosing regimens are initiated simultaneously and parallel enrollment is allowed in the multiple dosing regimens, the evaluation for Boin rule for each dose level and regimen would be made separately.

In [Table 4](#), if 1 out of 3 or 4 subjects experience a DLT in the first cycle of treatment, the algorithm recommends dose de-escalation, rather than staying at the current dose. Considering only information from 3 to 4 subjects will be initially available, the incidence of 1 DLT does not sufficiently establish that the MTD is exceeded. Under this situation, a recently published i3+3 design recommends staying in the current dose level if the observed number of DLTs is only 1 greater than the number required for dose escalation. Therefore, the Safety Review Committee could decide to enroll an additional 3 subjects at that dose level, if only 1 of 3 or 4 subjects experiences a DLT.

Formatted: C-[Hyperlink](#)

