### 3.2.2. Dose-Limiting Toxicity Definition

Dose-Limiting Toxicity (DLT) is defined in this study as a non-hematologic adverse event or abnormal laboratory value assessed as unrelated to disease progression, intercurrent illness, or concomitant medications and occurring during the first 28 days on study that meets any of the following criteria, using the Common Terminology Criteria for Adverse Events (CTCAE) grading system, version 5.0:

- Hematologic DLT is defined as CTCAE Grade 4 neutropenia (absolute neutrophil count  $<0.5 \times 10^9 /L$ ) or thrombocytopenia (platelet count  $<25.0 \times 10^9 /L$ ) lasting for 42 days or more from Cycle 1 Day 1 in the absence of residual leukemia (i.e., with less than 5% blasts by morphology or residual leukemia by flow-cytometry).
  - Anemia will not be considered for the definition of DLT.
- CTCAE Grade 3 AST (SGOT) or ALT (SGPT) increased for at least 7 days or Grade 3 hyperbilirubinemia for at least 7 days.
- CTCAE Grade 3 AST (SGOT) or ALT (SGPT) increased accompanied by Grade 2 bilirubin increase
- CTCAE Grade 4 AST (SGOT) or ALT (SGPT) increased of any duration
- Any other non-hematological adverse events that are CTCAE Grade 3 or 4. However, the following adverse events are NOT considered DLTs:
  - Grade 3 nausea, vomiting and diarrhea will be considered DLT only if not controlled to Grade 2 or lower with optimal therapy within 72 hours (not including tube feeding, total parenteral nutrition, and/or hospitalization). Any Grade 3 gastrointestinal toxicity requiring tube feeding, total parenteral nutrition, and/or hospitalization and any Grade 4 gastrointestinal toxicity will be considered DLT.
  - Grade 3 or 4 biochemical abnormalities (e.g., lipase or amylase increased) will only be considered DLT if accompanied by clinical consequences.
  - Grade 3 or 4 isolated electrolyte abnormalities must be without clinical consequence and resolve, with or without intervention, to less than Grade 2 levels within 72 hours.
  - Grade 3 infusion reaction if successfully managed and which resolves within 72 hours
  - Grade 3 or 4 Tumor Lysis Syndrome if it is successfully managed clinically and resolves within 7 days without end-organ damage

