### 3.2.4.3. Sub-Study PK Evaluability Criteria

Subjects should meet the following minimum criteria to be considered evaluable for the food effect assessment. PK non-evaluable subjects will be replaced.

- On Cycle 1 Day 8 and Cycle 1 Day 18, subject takes DS-1594b according to the assigned dose.
- Subject has an interpretable PK profile following administration of the assigned dose of DS-1594b on Cycle 1 Day 8 and Cycle 1 Day 18.
- Subject takes DS-1594b under the assigned dose and prandial conditions (first 7 days under fed state, then under fasted state afterwards) for at least 5 consecutive days prior to full PK sampling days on Cycle 1 Day 8 and Cycle 1 Day 18.
- Subject does not vomit within 4 hours after DS-1594b dosing on full PK sampling days.

For toxicity monitoring in each group of the DDI sub-study and food effect sub-study we will use the elimination boundaries in [Table 4](#)[Table 4](#) for BOPN design.

Formatted: C-Hyperlink

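### For subjects who enter the DDI sub-study before MTD declaration, the Table 4 boundary covers none of the 10 days on posaconazole for non-hematologic toxicity

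*Combined protocol and SAP*

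**What the plan says.** Section 3.2.3.2 describes two routes into the posaconazole part of the DDI sub-study.

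- **After MTD declaration:** DS-1594b alone on Cycle 1 Days 1-8, then with posaconazole on Cycle 1 Days 9-18.
- **Before MTD declaration**, from the third escalation cohort: the Note opens this route "If the use of posaconazole is essential for subject care during the dose escalation phase". To keep clear of the DLT evaluation period, the subject takes DS-1594b alone throughout Cycle 1. Posaconazole follows in Cycle 2, given "with 300 mg oral posaconazole twice on Cycle 2 Day 1 and once daily on Cycle 2 Day 2 to Cycle 2 Day 10". These subjects count toward the planned total of about 12. Voriconazole is not allowed on this route.

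The toxicity rule is at the end of Section 3.2.4.3: "For toxicity monitoring in each group of the DDI sub-study and food effect sub-study we will use the elimination boundaries in" Table 4. No counting window is given there. The note to Table 4 says that the number "of DLT is the number of subjects with at least 1 DLT in the first 28 days of dosing". Section 3.2.2 requires a DLT to be "assessed as unrelated to disease progression, intercurrent illness, or concomitant medications and occurring during the first 28 days on study". Sections 3.2 and 9.4.1.3 give the same 28-day period.

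Two provisions reach further. The hematologic DLT criterion in Section 3.2.2 looks at cytopenia lasting 42 days or more from Cycle 1 Day 1. The same section restarts the DLT period at the first dose of venetoclax or mini-HCVD when that dose is delayed, but only in Phase 2 Cohorts C and D.

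**The concern.** The plan gives each DDI group a numerical stopping boundary, yet for early entrants the exposure of interest begins the day after the count closes. Moving posaconazole to Cycle 2 protects the escalation data, and that choice is sound. The sub-study's own boundary, however, still refers to the first 28 days. Followed exactly, the rule would score such a subject on a cycle of DS-1594b alone and then be blind to non-hematologic DLT-type events while the strong CYP3A inhibitor is on board. A group could look clean against Table 4 even though toxicity under co-administration had occurred in subjects who entered early.

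**Working it through.** No DLT rate is needed. The check is a calendar comparison, after confirming what the boundary is.

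**1. The boundary itself.** Section 3.2 gives the elimination rule: Pr(p > 0.2 | data) > 0.95 under a uniform prior. For y DLTs in n subjects the posterior is Beta(1+y, 1+n−y), so the boundary is the smallest y with 1 − BetaCDF(0.2; 1+y, 1+n−y) > 0.95.

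- n = 3: y = 1 gives 0.819 and y = 2 gives 0.973, so the boundary is 2.
- n = 6: y = 2 gives 0.852 and y = 3 gives 0.967, so the boundary is 3.
- For n = 3 to 9 the results are 2, 3, 3, 3, 4, 4, 4, which is the elimination row of Table 4.

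The boundary is correctly computed. The issue is which events enter y.

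**2. Study days.** A cycle is 28 days (Section 5.1.2). If Cycle 2 starts without delay, Cycle 2 Day d is study Day 28 + d.

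- First posaconazole dose, early entrant: 28 + 1 = Day 29.
- Last posaconazole day, early entrant: 28 + 10 = Day 38.
- A late start to Cycle 2 would move these days further from the window.

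**3. Overlap with the non-hematologic count (Days 1-28).**

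| Route | Posaconazole days | Co-administration days inside the count | Days counted from first posaconazole dose |
|---|---|---|---|
| Before MTD declaration | 29-38 | 0 of 10 | 0 |
| After MTD declaration | 9-18 | 10 of 10 | 28 − 9 + 1 = 20 |

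The 20 days on the second route are Days 9-18 (10 on posaconazole) and Days 19-28 (10 after it).

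**4. Hematologic criterion.** Its 42-day horizon from Cycle 1 Day 1 extends past Day 38, so prolonged cytopenia is still caught. The gap is limited to non-hematologic events.

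**5. A window of equal length.** Twenty days from Day 29 ends on Day 29 + 20 − 1 = Day 48, which is Cycle 2 Day 20. It holds the same 10 days on posaconazole (29-38) and 10 days after (39-48).

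**The case against.** The calendar fact is hard to dispute. One could argue that Section 3.2.4.3 borrows only Table 4's numbers and not its window. That does not help, because Section 3.2.2 builds the 28 days into the definition of a DLT and no other window is offered for the sub-study.

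The serious objections concern size, and most of them stand.

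- **Early entry may never happen.** It requires an essential need for posaconazole and opens only from the third escalation cohort.
- **The repaired rule may have little to act on.** Table 4 starts at three subjects and is indexed by subjects at the current dose. With fewer than three early entrants at a dose, judged on their own, it gives no boundary.
- **Other protection continues on Days 29-38.** QTc rules (Table 12), hepatic interruption rules (Section 6.2.3.2), reporting of adverse events of special interest, ECGs on Cycle 2 Day 10 or 11 (Table 20), SRC oversight, and the study-termination provision in Section 8.9.2 all apply. A reader might infer that these subjects are unmonitored, or that stopping would rest on judgement alone. The documents do not support either inference. What is absent is the group count.

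Two further stronger readings are tempting. First, a reader might infer that early entrants run at higher exposure than later ones: they may keep the assigned dose "provided that dose level has been declared safe from the DLT evaluation, or at one dose level lower", whereas for later entrants the plan says: "Nonetheless, the dose will be at least 50% below the declared RP2D". These doses have different reference points. A cleared escalation level may lie well below the eventual RP2D, and the one-level-lower option reduces the dose further, so the exposures cannot be ranked from the documents. Second, a reader might want the lost probability of crossing the boundary. The documents give no DLT rate under co-administration and no number of early entrants. They also do not say whether subjects at different doses form one group. Any such figure would describe the assumptions rather than the plan.

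**Conclusion.** The point holds as a minor gap in the group-level safety rule. As written, the Table 4 boundary covers 0 of 10 co-administration days for non-hematologic toxicity in a subject who enters before MTD declaration, against 10 of 10 for one who enters afterwards. This rests on reading the 28-day window as it stands in Table 4 and Section 3.2.2, and it matters only if early entry is used. The 10 of 10 is calendar coverage. Whether each event would count also depends on how the concomitant-medication exclusion in Section 3.2.2 is applied when an azole raises DS-1594b toxicity, and the text does not say.

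Placing posaconazole in Cycle 2 is not at fault, the escalation data are unaffected, and the voriconazole group is unaffected. The case for changing the text is that the stated rule, followed to the letter, misses the period it is meant to watch in these subjects, and that correcting it is cheap.

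**What to change.** In Sections 3.2.3.2 and 3.2.4.3, state that for subjects entering the DDI sub-study before MTD declaration:

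- the posaconazole-group boundary counts events meeting the DLT criteria from the first posaconazole dose on Cycle 2 Day 1 through at least Cycle 2 Day 20 (Days 29-48), and the whole of Cycle 2 would also be acceptable;
- their Cycle 1 events feed only the BOIN tally, which is unchanged.

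Three clarifications would help but are optional: whether DS-1594b toxicity raised by an azole is exempt from the concomitant-medication exclusion in DDI monitoring, whether posaconazole subjects at different DS-1594b doses form one group, and what the SRC does when a group has fewer than three subjects.

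The cost is wording and slightly more safety tabulation. Adverse events, Cycle 2 laboratory tests and the Cycle 2 Day 10 or 11 ECGs are already collected, so no subjects or visits are added. Days 29-48 match the later entrants' window in length but not in intensity: Section 8.3 schedules laboratory tests twice weekly in Cycle 2, against at least three times weekly in Cycle 1.

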### **3.2.3.3. Sub-Study PK Evaluability Criteria**

Subjects should meet the following minimum criteria to be considered evaluable for the DDI assessment. PK non-evaluable subjects will be replaced.

- On Cycle 1 Day 8 and Cycle 1 Day 18 (or Cycle 2 Day 10 for subjects entering DDI sub-study before MTD declaration), subject takes DS-1594b according to the assigned dose.
- Subject has an interpretable PK profile following administration of the assigned dose of DS-1594b on Cycle 1 Day 8 and Cycle 1 Day 18 (or Cycle 2 Day 10).
- Subject does not vomit within 4 hours after receiving either dose of DS-1594b or antifungal agents (posaconazole or voriconazole) on PK sampling days.
- Subject receives at least 5 consecutive twice daily or daily doses of DS-1594b at the assigned dose prior to the co-administration with antifungal agents
- Subject receives at least 5 consecutive twice daily or daily doses of DS-1594b at the assigned dose when co-administered with antifungal agents
- Subject receives the assigned dose and appropriate prandial condition of the antifungal agents.

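### DDI sub-study: the five-dose evaluability runs are not tied to the PK sampling days, so a profile off steady state can meet every dosing-history criterion

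*Combined protocol and SAP*

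**What the plan says.** Section 3.2.3.2 sets out to measure the effect of repeated doses of antifungal agents "that are strong CYP3A inhibitors, on the steady-state PK of DS-1594b". On the antifungal side it states: "The anti-fungal agents are planned to be given for 10 consecutive days as stated above to ensure steady-state is reached". Section 9.4.9.2 analyses AUCtau and Cmax as the geometric mean ratio of Cycle 1 Day 18 (or Cycle 2 Day 10) to Cycle 1 Day 8. About six subjects are planned per antifungal.

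Section 3.2.3.3 decides who enters that ratio, because non-evaluable subjects are replaced. Its dosing-history criterion for the reference period is: "Subject receives at least 5 consecutive twice daily or daily doses of DS-1594b at the assigned dose prior to the co-administration with antifungal agents". For the azole period the counterpart criterion reads: "Subject receives at least 5 consecutive twice daily or daily doses of DS-1594b at the assigned dose when co-administered with antifungal agents".

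The remaining criteria are:

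- on the PK days, "subject takes DS-1594b according to the assigned dose";
- as to profile quality, "Subject has an interpretable PK profile following administration of the assigned dose of DS-1594b on Cycle 1 Day 8 and Cycle 1 Day 18", with Cycle 2 Day 10 replacing Day 18 for pre-MTD entrants;
- no vomiting within 4 hours of dosing on PK days;
- the antifungal's assigned dose and prandial condition.

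Section 9.4.1.4 refers back to this list and adds no dosing rule.

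The food-effect sub-study has the same single-sequence Day 8 / Day 18 structure. Section 3.2.4.3 requires its assigned dose and prandial condition "for at least 5 consecutive days prior to full PK sampling days on Cycle 1 Day 8 and Cycle 1 Day 18".

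**The concern.** Neither DDI run has an anchor. Five doses are also only 2.5 days on BID. Two kinds of subject can pass the dosing-history criteria with a profile that is not at steady state:

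- **Azole period.** A BID subject takes five doses on Days 9–11, later misses doses or has them held, and takes the assigned dose on Day 18. Missed doses are not replaced (Section 5.1.2), and Table 11 allows a held drug to resume at the prior dose in some cases.
- **Reference period, pre-MTD entrants.** Section 3.2.3.2 gives them DS-1594b alone for all of Cycle 1, but Table 18 takes the reference profile on Day 8. Five doses taken after Day 8 still precede co-administration, so they qualify a profile already drawn.

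Section 3.2.3.1 says the sub-study is to identify the DS-1594b regimen that can be given with antifungals. With about six subjects per antifungal, one or two such profiles can move the estimate materially. Section 2.4.2 reports QTc prolongation in monkeys, so an understated rise in exposure would matter.

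**Working it through.** The plan states no precision or sample-size derivation for this sub-study, so there is no figure to reproduce. The check asks how far an admitted profile can lie from the steady-state ratio.

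**Inputs from the documents:** half-life 7 to 8 h (Section 3.1); expected exposure increase of 30% with posaconazole and 2-fold with voriconazole, so true ratio R = 1.3 or 2.0 (Section 3.2.3.2); BID or QD dosing; n of about 6 per antifungal.

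**Assumptions:** one compartment, first-order absorption with ka 0.5 to 2 per h, and an azole that lowers clearance only, so k falls to k/R.

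**Formula.** The fraction of a single dose's total AUC that falls in the first t hours is

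f(t, k) = 1 − [ka·e^(−kt) − k·e^(−ka·t)] / (ka − k).

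Steady-state AUCtau equals single-dose total AUC, so relative to steady state on Day 8:

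- Day 18 profile after full washout: R × f(τ, k/R)
- Only the last dose before the PK day missed: R × {1 − [f(2τ, k/R) − f(τ, k/R)]}

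**Worked case: BID (τ = 12 h), half-life 7.5 h, ka = 1, R = 1.3.** k = 0.693/7.5 = 0.0924 and k/R = 0.0711.

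- f(12) = 1 − 0.4261/0.9289 = 0.541; f(24) = 1 − 0.1816/0.9289 = 0.805.
- Washout: 1.3 × 0.541 = 0.70.
- One missed dose: 1.3 × (1 − 0.263) = 0.96.

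For R = 2.0 the same steps give 2 × 0.398 = 0.80 and 2 × (1 − 0.256) = 1.49.

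**Ranges over half-life 7–8 h and ka 0.5–2 per h:**

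| Apparent AUCtau ratio | True 1.3 | True 2.0 |
|---|---|---|
| BID, last dose missed | 0.93–0.98 | 1.45–1.51 |
| BID, full washout | 0.63–0.76 | 0.70–0.87 |
| QD, full washout | 1.00–1.08 | 1.23–1.38 |

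If the azole acted through bioavailability instead (half-life unchanged), the BID voriconazole washout ratio would be 1.15–1.36, which is not reversed.

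Cmax is also a primary parameter of the ratio. On QD with the longest gap, the clearance model gives Cmax ratios of about 0.90–0.94 (posaconazole) and 0.95–1.01 (voriconazole). With no doses missed they would be 1.12–1.16 and 1.42–1.55.

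**Effect on the six-subject ratio:** R × (r/R)^(m/6), with m affected subjects at apparent ratio r, on BID.

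- One washed-out subject: 1.15–1.19 instead of 1.30; 1.68–1.74 instead of 2.00.
- Two washed-out subjects: 1.02–1.09 and 1.41–1.51.
- One subject missing only the last dose: 1.3 × (0.93/1.3)^(1/6) = 1.23 to 1.3 × (0.98/1.3)^(1/6) = 1.24; likewise 1.90–1.91 for a true 2.0.

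**Opposite direction.** If Day 8 is a first-dose profile and the azole-period profile is at steady state, the ratio is R / f(12, k). At the central values f(12, k) = 0.637, so a true 1.30 becomes about 2.0 and a true 2.00 about 3.1. Pre-MTD entrants receive posaconazole only, so the first figure is the relevant one for them.

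**With an anchored five-day run.** BID gives 10 doses plus the PK-day dose. The fraction of steady state is about 1 − 2^(−11 × 12/15) = 99.8% for voriconazole (half-life 15 h under a halved clearance) and above 99.9% for posaconazole.

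**The case against.** **The interpretable-profile criterion.** The list is headed as minimum criteria and includes an interpretable profile. Tables 17 and 18 take a pre-dose sample and, on BID, a 12-hour sample on the azole PK day. After a three-day hold the modelled pre-dose value is about 1% of the 12-hour value with posaconazole and 6–10% with voriconazole, whereas at steady state the two are equal. Sections 5.1.2 and 8.4.1 also have prior dose times recorded. A gross case would be visible, so it does not follow that such a subject must be counted as evaluable. But interpretable is undefined, no rule requires exclusion, and a single missed dose leaves a much smaller mark.

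**Natural reading.** If the reference run is read as leading straight up to Day 9, post-MTD BID subjects have three doses before the Day 8 dose, or 1 − 2^(−48/7.5), about 99% of steady state. That protects their Day 8 profile. It does not protect Day 18, or Day 8 in pre-MTD entrants. The food-effect criterion also lacks the word immediately, so it is better than the DDI wording but not watertight.

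**Missed doses may be rare.** Section 8.7 has the first cycle of DS-1594b administered at the site. Interruptions for Grade 3 QTcF prolongation (Table 12) or liver enzymes (Section 6.2.3.2) resume one dose level lower, so the assigned-dose criterion would already fail. This stands: the documents support no claim that interruption is likely. The Cycle 2 azole period of pre-MTD entrants falls outside the on-site first cycle.

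**Five BID doses as too little overlap.** A reader might infer that 2.5 days of joint dosing leaves inhibition incomplete. The documents do not support that. The antifungal's assigned dosing is a separate criterion, and five BID doses leading up to the PK-day dose still give about 1.29 and 1.90–1.94. The problem is the missing anchor, far more than the count.

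**Conclusion.** The point holds as a gap in the evaluability rule. Section 3.2.3.3 can admit profiles that do not answer the sub-study's steady-state question, and nothing else in the plan requires their exclusion. Per affected BID subject the distortion is large: one missed dose is enough to remove an expected 30% increase in AUCtau. On the six-subject ratio it is modest for one subject with one missed dose (1.23–1.24 against 1.30) and material for one or two washed-out profiles.

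Two stronger readings should be resisted. The rule does not generally reverse the azole effect: AUC reversal is confined to BID, and for voriconazole it also needs a long gap and the clearance mechanism. Nor is the bias always toward no interaction, since an affected Day 8 inflates the ratio. All of this depends on doses being missed, at a rate the documents do not give, and on the assumed absorption rate and mechanism. The ratio is a secondary objective, so the weight lies between a minor clarification and a change that should be made.

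**What to change.** Replace the two dose-count criteria in Section 3.2.3.3 with:

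- DS-1594b at the assigned dose for at least 5 consecutive days immediately before Cycle 1 Day 8; and
- DS-1594b and the antifungal, each as assigned, for at least 5 consecutive days immediately before Cycle 1 Day 18 (or Cycle 2 Day 10).

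Add the word immediately to the corresponding criterion in Section 3.2.4.3, so that the two sub-studies follow one rule.

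The cost is one protocol paragraph and one added word. A few more subjects may prove non-evaluable and need replacing, which Section 3.2.3.3 already allows. No extra samples are needed.
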